# **Objectives:**

The primary outcome measured in this study is post-operative pain with movement measured both during cough and 20° straight leg raise. Pain at rest will also be evaluated. All types of pain will be measured using a visual analogue pain scale (VAPS) determined using a 100mm line with the patient making a mark on the line between no pain and worst pain ever (12). Pain scores will be collected after the bolus of study medication/placebo (zero time), at PACU discharge (2hr), 6hr, 12hr, 24hr, 48hr, and 72hr post-cesarean section. Pain at 4-6 weeks and 3mo will be quantitated over the telephone using a numerical pain scale (NPS) with 0 being no pain and 10 being the worst pain imaginable. In addition to the pain scores, pain with movement will be further evaluated qualitatively using the short-form McGill pain questionnaire (22) at all time-points in the study. This will allow us to look at pain quality (sharp, burning, etc.), as well as examining the affective components (exhausting, fearful, etc.) of the pain.

There are several secondary outcomes of this study that can be divided into rescue medication information, medication side effects, breastfeeding, wound evaluation, patient satisfaction, and cost-analysis.

Rescue medication data will be collected during the hospitalization period (0-72hr). We will note the time to dosing with the first rescue medication for breakthrough pain. After the first rescue medication is given, the patients will be eligible for further doses of IV or

PO pain medicines for continued breakthrough pain as needed (see **Study Design and Methods** section below for specifics). The time to first opioid use for pain will also be recorded whether this entails IV or PO administration. Additionally, we will quantitate narcotic use in terms of morphine equivalents given (in mg) both by post-operative day and with a cumulative total. The total dose of NSAIDs (in mg) will be recorded for each of the first three postoperative days, along with a cumulative total. We will also be measuring the proportion of patients who require opioid supplementation at 0, 2, 6, 12, 24, 48, and 72 hours post-op. We will also ask if patients are still requiring opioids and/or NSAIDs for surgical discomfort along with inquiring about the amount of each used per day at the 4-6 week and 3 month follow-up telephone calls.

As several different medications are utilized within this study, it is important to monitor side effects of the medications, and see if these profiles change under the conditions of the study. We will collect data on the incidence and severity of opioid central and/or systemic side effects – pruritus, nausea/vomiting (not associated with hypotension), somnolence, and respiratory depression. Somnolence will be graded using a published perioperative somnolence scale (23). Measurements of nausea/vomiting and pruritus will make use of previously published scales (24). Respiratory depression will be considered to be present if the respiratory rate is < 10 breaths/min. We will also make note of both the type and amount of treatment given for these opioid-related side-effects. In addition, we will collect data on the incidence and severity of ropivacaine systemic side effects – tinnitus, perioral numbness, metallic taste, and seizures – and will characterize both the type and amount of treatment required.

Breast-feeding success and safety will be monitored during this study. Breast feeding success will be measured using LATCH Scores (25) obtained in the PACU, and once per shift on the mother-baby unit for 72 hours. These will be assigned by either the labor and delivery nurses or by the nurses in the post-partum ward. We will also assess the proportion of mothers breast-feeding their infants at 24, 48, 72hr, and during their 4-6 week and 3 month follow-up phone calls. Maternal plasma and breast milk concentrations have been measured during epidural analgesia with ropivacaine (0.125%)

for labor, with the breast milk-plasma ratio being somewhere between 0.23 and 0.25 at 18-24hr (26). Surprisingly, the literature is silent regarding the concentration of ropivacaine in human breast milk after continuous wound infusion.

Both the cesarean section incision and the catheter insertion site will be evaluated. Any catheter- or infiltrate-related issues like wound infection and seroma formation will be noted. Wounds will be assessed for infection or dehiscence at 24, 48, and 72hr. At the 4-6 week and 3-month follow-up phone calls the patient will be asked about the presence of wound dysesthesia (numbness, tingling, burning, pricking, allodynia, or hyperesthesia). The patient will also be asked about the occurrence of infection, dehiscence, and keloid formation at this time.

Patient satisfaction will be monitored with a satisfaction scores (100 mm scale) at 72hr. A cost analysis will occur for the inpatient stay. Some of the costs we will look at are include those for preparation of the drugs and devices, along with monitoring/supervision costs based on nursing and physician interventions, as well as cost of days spent in the hospital (27).

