risks of myocardial infarction, aneurysmal rupture, thrombophlebitis, post-operative atelectasis and pneumonia. Poorly controlled post-surgical pain relief also influences the risk of developing chronic post-surgical pain (CPSP) (5, 6). CPSP is defined as pain of at least 2mo duration which develops after a surgical procedure, and which is not related to any other causes of pain (infection, malignancy, etc.) or to pain continuing from a pre-existing pain problem (7). The incidence of CPSP after cesarean section is believed to be between 10-12% (5, 6), meaning that as many as 168,000 women might be affected with this each year. Even more troubling is that an estimated 4% of the women undergoing cesarean section (~48,000) actually develop disabling chronic pain defined as pain > 5 on a scale from 0 to 10 (6). Recognition of the above psychological and physical attributes of pain led to the Joint Commission recommendation to treat pain as the fifth vial sign, with the stated goal for US healthcare facilities to uniformly achieve pain scores  $\leq$  3 out of 10 (8).

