# **Participant Selection**

The study will take place at Emory University Hospital Midtown (EUHM), which cares for a mixed community- and university-based obstetric practice. Parturients will be recruited from the patient pools of both private and Emory physicians, and enrolled after appropriate consent has been obtained. The inclusion criteria for the study includes all ASA class I-III parturients at least 34 weeks pregnant, that are 18 years or older, have never had a cesarean section, have had one or two prior cesarean sections, and are undergoing scheduled or unscheduled non-emergent cesarean sections with spinal anesthesia. Exclusion criteria includes parturients who have allergies to morphine, ketorolac, or amide local anesthetics; pregnancies less than 34wks gestational age; significant maternal cardiac, liver, or renal disease; maternal history of narcotic abuse or dependency; presence of a pre-operative fever ( $\geq 100.4$  °F); emergent cesarean sections with or with-out general anesthesia; and patients in whom valid consent is questionable (non-English speakers or mentally-impaired individuals). Study patients have the option of withdrawing from the study at any point, as the On-Q® pump infusion can be simply discontinued and the catheter removed. At such time the patient would revert to our standard pain management protocol.

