There are possible benefits of being enrolled in the study. If our hypothesis is correct, both acute postoperative pain (at rest and with movement) and chronic postsurgical pain will be reduced in patients that receive the ropivacaine infusions. These patients would likely experience a reduction in the use of opioids and other adjunctive pain medicines. This could lead to a reduction in the incidence and treatment of medication-related side-effects. The reduction in pain, as well as a decrease in medication use, might result in more successful and safer breastfeeding. Pain and side-effect reduction might also lead to the need for fewer nursing interventions, along with a potential decrease in the length of stay after a cesarean section. If these goals are met, this truly multimodal technique of postoperative pain control might also decrease the cost of these patients' hospitalization.

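### Late pain and wound dysesthesia are collected with no pre-operative scar-symptom item, so symptoms persisting from an earlier cesarean cannot be told apart from new ones at 3 months

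*Combined protocol and SAP*

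**What the plan says.** Under Objectives, late pain is a telephone score: "Pain at 4-6 weeks and 3mo will be quantitated over the telephone using a numerical pain scale (NPS"). At the same calls, "the patient will be asked about the presence of wound dysesthesia (numbness, tingling, burning, pricking, allodynia, or hyperesthesia"). Neither item, as described, asks when the symptom began. The short-form McGill questionnaire, planned for every time-point, is described as covering the quality and affective side of pain, not its onset.

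The Introduction and Background gives the concept: "CPSP is defined as pain of at least 2mo duration which develops after a surgical procedure". It then rules out other causes, "or to pain continuing from a pre-existing pain problem (7"). It also gives a rate: "The incidence of CPSP after cesarean section is believed to be between 10-12% (5, 6").

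Participant Selection admits women who "have never had a cesarean section, have had one or two prior cesarean sections". The nearest exclusion to a pain history is narcotic abuse or dependency. Chronic pain and scar pain are not excluded.

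The first pain score comes after the study bolus. The Abstract calls this score the baseline, but it is taken at the end of surgery, after a spinal that the Study Design section says lasts 1.5-2hr. The description of the patient folder mentions no pre-operative pain sheet. The Statistical Analysis section names no adjustment for prior cesarean or prior pain.

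Patient Safety and Potential Benefits says that, on condition that the hypothesis is correct, "chronic postsurgical pain will be reduced in patients that receive the ropivacaine infusions".

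**The concern.** The plan's concept of chronic post-surgical pain needs two facts about each woman: how long the pain has lasted, and whether it was there before this operation. The late data as described supply neither directly. For a first cesarean the gap is small, because there is no earlier cesarean scar. For a repeat cesarean it matters: lasting pain or numbness at the old scar is the kind of symptom the calls will pick up, and it was there before any infusion began.

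At stake is the meaning of the late secondary results. Any statement about chronic pain or wound dysesthesia after this surgery would mix new symptoms with carried-over ones. Once surgery has taken place, pre-operative status can only be recalled.

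**Working it through.** **The plan's own figures.** No sample size, power or case rule is given for chronic pain, so there is no design figure to reproduce. The Introduction does give a national count. About 4 million deliveries × 30% = 1.2 million cesareans, and 10-12% of these is 120,000-144,000. The stated upper figure of 168,000 corresponds to 168,000 / 1,200,000 = 14%. This side discrepancy barely affects what follows, as shown below.

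**Inputs.**
- p, new chronic pain after a cesarean: 10-12% (Introduction).
- Arm size: 20, three arms (Statistical Analysis).
- r, share of repeat cesareans: **assumed** 25-75%; the documents give no figure.
- k, share of earlier chronic pain still present: **assumed** 50-100%; the documents give no figure.
- Effect: a 40% relative reduction in new chronic pain, **assumed** by borrowing the effect size that the plan states for pain scores.

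**Formulas.** Each repeat-cesarean woman is treated as having had one earlier cesarean, and old and new pain as independent.
- Old pain rate: o = r × p × k, the same in every arm.
- Observed control rate: c = 1 − (1 − p)(1 − o).
- Observed treated rate: t = 1 − (1 − 0.6p)(1 − o).
- Apparent relative reduction: 1 − t/c.
- Share of control cases with old pain only: o(1 − p)/c.

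| p | r | k | o | Old pain per arm (20 × o) | c | t | Apparent reduction | Old pain only |
|---|---|---|---|---|---|---|---|---|
| 10% | 25% | 50% | 1.25% | 0.25 | 11.1% | 7.2% | 35.5% | 10.1% |
| 10% | 50% | 100% | 5.0% | 1.0 | 14.5% | 10.7% | 26.2% | 31.0% |
| 10% | 75% | 100% | 7.5% | 1.5 | 16.8% | 13.1% | 22.1% | 40.3% |
| 12% | 25% | 50% | 1.5% | 0.3 | 13.3% | 8.6% | 35.5% | 9.9% |
| 12% | 75% | 100% | 9.0% | 1.8 | 19.9% | 15.6% | 21.9% | 39.8% |

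Across the trial, 60 × o runs from 0.75 to 5.4 women. The chance of at least one such woman, 1 − (1 − o)^60, runs from 53% to over 99%. For comparison, a control arm expects 20 × 0.10 = 2.0 to 20 × 0.12 = 2.4 new cases.

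**What drives these numbers.** Put s = r × k. The old-only share becomes s(1 − p) / [1 + s(1 − p)], so p enters only through (1 − p). At p = 14% the range is 0.1075/1.1075 = 10% to 0.645/1.645 = 39%, practically the same. The share therefore comes from the two assumed inputs, not from the plan's 10-12%.

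**Power.** For 20 against 20 at a two-sided 0.05, power to detect the assumed 40% reduction is about 7% when only new pain is counted, and 5-7% with old pain mixed in.

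**The case against.** Several objections have force.

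- **Chronic post-surgical pain is not a declared endpoint.** The definition is background and the expected benefit is conditional. The outcome lists name a pain score, dysesthesia and drug use, with no case rule. This stands. A reader might infer that the plan has a chronic-pain endpoint that breaks its own definition, or that it treats the 4-6 week call as chronic pain. The documents say neither. The gap is that the late data cannot be read in the sense the plan itself gives to the term.
- **Allocation is randomized and double-blind.** This stands too. A reader might infer that old pain favors one arm, but it is balanced in expectation. Chance imbalance at 20 per arm is a feature of any unmeasured baseline factor, and the test allows for it. What randomization does not remove is the dilution, the inflated rate and the extra noise.
- **The late comparison is uninformative anyway.** For a yes/no chronic-pain outcome this is right: the fix corrects what is measured and does not rescue power. The late data will still be collected, so they should be interpretable.
- **The attached Data Collection Instrument might hold a pre-operative item.** It is not in the text available, so this cannot be ruled out. Nothing in the protocol mentions such an item or uses one in analysis.
- **Some late items are already worded around this surgery.** Drug use is limited to surgical discomfort, and keloid is asked about as an occurrence. This narrows the point to the pain score and dysesthesia, whose wording does not separate this operation from an earlier one.

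**Conclusion.** The point holds as a gap in interpretability for secondary outcomes. With repeat cesareans eligible and no pre-operative scar-symptom item described, a persisting symptom from an earlier cesarean would be recorded at 3 months like a new one. The consequences are a diluted difference, inflated rates of chronic pain and dysesthesia, and added noise, with no expected bias toward any arm.

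The size is unknown. Under the assumed ranges, 0.25 to 1.8 women per arm carry old pain in, and a true 40% reduction would appear as 22-36%. These figures illustrate what the gap could do. A reader might take the 10-40% old-only share as an estimate for this trial, but it rests on an assumed repeat share and an assumed persistence, neither of which the documents give.

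The primary 0-72hr comparison and the 20 per arm do not depend on any of this. The change is worth making because it is cheap and cannot be made well after surgery.

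**What to change.** **Before the spinal, once.** Ask whether the woman has had persistent pain or dysesthesia at a previous cesarean scar that predates this pregnancy's late discomfort or labor. Record yes or no, a 0-10 score if yes, and the same dysesthesia checklist that is used at the calls.

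**At both calls.** Ask for pain at the cesarean wound specifically, and whether it is new since this surgery.

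**In reporting.** Present 3-month wound pain and dysesthesia as new-onset or worsened relative to the scar-specific pre-operative answer, alongside the raw scores. Use only the 3-month call for any statement about chronic post-surgical pain, since 6 weeks falls short of the 2-month threshold.

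**What to avoid.** Do not subtract a general abdominal or pelvic pain score taken at consent. Participants are at least 34 weeks pregnant and some have unscheduled cesareans, so pregnancy or labor pain would raise that score and mask new wound pain. For example, a woman scoring 6 at consent and 4 at the wound at 3 months would count as no case.

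**Cost.** About a minute of extra questions at consent and a slightly lower count of chronic cases. Treatment and sample size do not change. If the Data Collection Instrument already holds such an item, citing it in the protocol and adding the reporting rule and the onset question would suffice.

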### **IRB** Protocol

### Multimodal Post-Cesarean Analgesia with Spinal Morphine and Continuous Wound Infiltration of Ropivacaine Using the OnQ® Elastomeric Pump: A Dose-Ranging Study Using a High-Volume, Low-Dose Protocol PI: [name]

Abstract:

The purpose of the proposed study is aimed to determine whether continuous subfascial infusion of ropivacaine using the On-O® elastomeric pump in combination with intrathecal (IT) preservative-free morphine (PFM) will improve post-operative cesarean section pain relative to IT PFM alone (the current standard of care). Using a doubleblinded, randomized, placebo-controlled study design, 60 women undergoing their first, second or third cesarean section will be randomly assigned to one of 3 different groups receiving either saline (control, n=20) or ropivacaine (0.1% or 0.2%, experimental groups n=20 in each) subfascially via the elastomeric pump. We will enroll up to 70 subjects to achieve 60 randomized and treated subjects, to account for screen failures and/or early terminations, All participants will receive an IT dose of 200mcg of PFM as part of a standardized spinal anesthetic for their operative procedure. During closure of their abdomen, all patients will undergo placement of a multi-orifice, silver-impregnated catheter in the subfascial space. At the conclusion of the surgery, the catheter will be bolused with 8ml of one of the three test solutions, after which an On-O® elastomeric pump (containing the same solution as initially administered through the catheter) will be attached to infuse the test solution at a rate of 8ml/hr. The infusion system will then be left in place for up to 72hr. Adjunctive pain medicines (ketorolac, morphine, ibuprofen, and oxycodone-acetaminophen) will be available for the treatment of breakthrough pain during hospitalization. The primary outcome being measured in the study is postoperative pain with movement as assessed immediately after the study bolus (baseline) and during the immediate post-operative period, when leaving the PACU (2hr), 6hr, 12hr, 24hr, 48hr, and 72hr post-op. Pain will also be evaluated by telephone at 4-6 weeks and 3mo after surgery. A visual acuity pain scale (VAPS) will be used to measure patient pain levels while hospitalized whereas pain at the 4-6 week visit and 3mo will be quantitated using a numeric pain scale (NPS). Secondary outcomes to be studied include degree of pain at rest, time to first rescue medication, time to first opioid use, amount of

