To date, long-acting neuraxial opioids like PFM provide the gold standard for postcesarean delivery analgesia whether given via the IT or epidural route, providing excellent pain relief for the first 24hr while allowing the mother to ambulate and care for her child (18, 19). However, it is clear that neuraxial opioids do not provide complete analgesia for cesarean section when used as primary agents, with more than 70% of patients requesting further analgesia (19). Even when codeine with acetaminophen is given prn, 33% of women in one study still experienced inadequate analgesia (18). Pain with movement appears to be the most poorly treated pain phenomenon using neuraxial PFM (19). Again, this points to the importance of multimodal pain control in obstetric patients. Surprisingly, while continuous wound infiltration has been examined as a primary technique for post-cesarean pain relief (13,14,15,16) and has even been compared for efficacy to epidural (13,14) and IT (17) post-cesarean analgesia, no one has tested to see if continuous wound infiltration with LAs improves the analgesia obtained from IT PFM. However, it is standard practice of some obstetricians in our institution to use the continuous wound infiltration system on every patient undergoing a cesarean section whether they have IT PFM or not. The purpose of the proposed study is to examine the hypothesis that continuous wound infusion with ropivacaine using a highvolume, low-dose protocol will significantly improve pain with movement after cesarean section in patients who have received our standard dose of IT PFM. A control group (IT PFM + saline wound infusion) will be compared to two groups receiving both IT PFM along with one of two doses of ropivacaine (experimental groups) using the OnQ® elastomeric pump for delivery of the infusions. We have purposefully used lower concentrations of ropivacaine (0.1-0.2%) along with higher volumes in recognition that the nerves to be anesthetized are of smaller diameter, and therefore require lower concentrations of LA for this effect; while ensuring a high enough volume to completely

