# **Statistical Analysis**

Based on a preliminary sample size calculation using an  $\alpha$  risk of 0.05, a  $\beta$  risk of 0.2, and an effect size involving a 40% reduction in pain scores, we estimate that 20 patients are needed in each arm of the study. Data normality will be tested using the Kolmorgorov-Smirnov test. Normally distributed data will be presented as means  $\pm$  SD, whereas non-normally distributed data will be expressed as medians with interquartile ranges. Categorical data will be reported as frequencies. VAS scores will be analyzed using two-way ANOVA for repeated measures. Non-normal data will be analyzed using the Friedman test. Categorical data will be analyzed using the X test. Multiple comparisons will use a Bonferroni correction. Differences will be considered statistically significant at a P<0.05.

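### The plan names no valid analysis or censoring rule for time to first rescue and time to first opioid, two right-censored secondary outcomes

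*Combined protocol and SAP*

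**What the plan says.** The Abstract and the Objectives section list both times as secondary outcomes. On rescue: "We will note the time to dosing with the first rescue medication for breakthrough pain". On opioids: "The time to first opioid use for pain will also be recorded", by either route. The collection window is 0-72 hr.

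Rescue is given on request or for a pain score above 3 (Study Design and Methodology). Women may withdraw at any time (Participant Selection), and the catheter section of Patient Safety allows for discharge as an end point of the infusion. Never needing the drug, or leaving before needing it, is therefore possible by design.

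The Statistical Analysis section is the whole plan. It has a normality test, a repeated-measures ANOVA for VAS scores, chi-square for categorical data, a Bonferroni correction, and, for everything that is not normal, this: "Non-normal data will be analyzed using the Friedman test". The threshold is: "Differences will be considered statistically significant at a P<0.05". Kaplan-Meier, log-rank and Cox methods do not appear, nor does a censoring rule or a rule for women with no event.

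**The concern.** These are time-to-event outcomes in a plan with no time-to-event method. Times to a first dose are usually skewed, so the plan's own rule sends them to the Friedman test. That test ranks several related values within each subject. Here there are three independent groups and one time per woman, so it cannot be applied. If the times passed the normality test, no test is named for them, because ANOVA is reserved for VAS scores. Chi-square can compare ever-use but discards when use began.

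The analyst will therefore have to choose a method that is not in the plan, possibly after seeing the data. One easy choice, with blank cells in a spreadsheet, is to compare only the women who have a time. That conditions on the outcome: the better ropivacaine works, the more women leave its arm, and those who leave are its best responders.

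**Working it through.** **The plan's own figure.** The plan gives no power for these outcomes. Its sample size ("we estimate that 20 patients are needed in each arm of the study") is for pain scores, with a "risk of 0.2, and an effect size involving a 40% reduction in pain scores". No SD or control mean is given, so it cannot be rebuilt. At 20 per arm the detectable standardised difference is √(2/20) × (1.960 + 0.842) = 0.886, so a 40% reduction fits only if SD/mean is about 0.40/0.886 = 0.45. This does not bear on censoring; only the 20 per arm is used below.

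**Inputs.** From the documents: 20 per arm, 72 hr window, 0.05 (taken as two-sided). Assumed: proportions using an opioid by 72 hr, constant hazards and no early censoring. The 70% used for saline borrows a background figure ("with more than 70% of patients requesting further analgesia" in the Introduction). That figure concerns any further analgesia after neuraxial opioid, with no time window, so here it is only an assumption.

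**What a users-only comparison looks at.** Take 70% versus 40%.
- Hazard ratio = ln(0.60)/ln(0.30) = 0.511/1.204 = 0.42.
- Expected users: 20 × 0.70 = 14 and 20 × 0.40 = 8. Excluding the rest removes 6 saline women and 12 ropivacaine women.
- Mean time among users = 1/λ − 72(1−p)/p, with λ = −ln(1−p)/72. Saline: 59.8 − 30.9 = 28.9 hr. Ropivacaine: 140.9 − 108.0 = 32.9 hr. Difference 4.0 hr.
- Mean time over all women, counted up to 72 hr, = p/λ. Saline: 0.70 × 59.8 = 41.9 hr. Ropivacaine: 0.40 × 140.9 = 56.4 hr. Difference 14.5 hr.

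**Power, one ropivacaine arm against saline (simulation, %).**

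| Opioid use by 72 hr | HR | Log-rank | Users only, t-test | 72 hr assigned, t / rank | Chi-square on ever-use | Log-rank at 0.025 |
|---|---|---|---|---|---|---|
| 70 v 40 | 0.42 | 51 | 8 | 44 / 48 | 45 | 38 |
| 70 v 30 | 0.30 | 76 | 9 | 68 / 73 | 71 | 66 |
| 90 v 60 | 0.40 | 71 | 17 | 66 / 64 | 64 | 62 |

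Entries are good to about 2-3 points. Allowing for that, assigning 72 hr costs about 3-9 points. Formula check of the first row: 22 expected events give √(22/4) × 0.858 − 1.960 = 0.05, or 52% power; at 0.025, 2.012 − 2.241 = −0.23, or 41%.

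**Sensitivity.**
- With 20% of women censored early, the users-only analysis still had by far the lowest power.
- If rescue is nearly universal on saline (98% by 72 hr) and the hazard ratio is 0.35, log-rank has 87%, users-only 45% (t) or 40% (rank), and 72 hr assigned 85% or 77%. The loss is smaller but not trivial.
- If ropivacaine changes only whether a woman uses the drug and not when, assigning 72 hr costs about 7-29 points against log-rank.

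**The case against.** A reader might infer that the plan drops women who never need the drug, or gives them an invented value. It says neither; it is silent. A reader might also infer that the opioid-sparing effect is largely lost. That holds only for these two outcomes, and only if non-users are excluded. Assigning 72 hr keeps most of the power in the three tabulated scenarios.

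Opioid sparing is also measured in other ways. The Objectives section plans morphine equivalents by day and in total, where a non-user followed to 72 hr has a true value of 0 mg. It also plans the proportion needing opioid at seven time points, which chi-square suits at any one of them. On ever-use by 72 hr, chi-square has 45-71% power where log-rank has 51-76%.

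The assumptions are open to challenge too. The opioid rate in this trial is unknown, since the first request is met with ketorolac. The rescue regimen changes at 24 hr, which a constant hazard does not reflect. For first rescue, censoring may be light.

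All of this stands and limits the size of the point. It does not supply a valid test for the two outcomes. The Friedman mismatch affects other single-value skewed outcomes as well, so it is not peculiar to censoring, but here no named alternative fits the times.

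**Conclusion.** The gap is real: two named secondary outcomes are right-censored, and the plan's only rule for skewed non-VAS data cannot compare independent arms or handle censoring. It should be fixed, but it does not touch the primary outcome.

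The cost depends on what the analyst does. Excluding non-users cuts power from 51-76% to 8-17% under the tabulated assumptions; assigning 72 hr costs about 3-9 points there, and more if the drug affects only whether opioid is used. These figures rest on assumed event rates and constant hazards.

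A correct method will not make these outcomes well powered. With Bonferroni for two comparisons, log-rank power is about 38-66% in the same scenarios. For 80% power at 0.05, a hazard ratio of 0.5 needs 66 events, more than the 40 women in a pairwise comparison.

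**What to change.** Add to Statistical Analysis, for time to first rescue and time to first opioid:
- time runs from the study bolus, which is already time zero for the pain scores;
- every randomised and treated woman is included;
- a woman without the event is censored at 72 hr, discharge or withdrawal, whichever comes first;
- each ropivacaine arm is compared with saline by Kaplan-Meier curves and the log-rank test, with a Cox model for the hazard ratio;
- the plan's Bonferroni correction applies to the two comparisons (0.05/2 = 0.025 each).

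Note in the text that discharge and withdrawal may depend on pain, so censoring there may be informative, and report the numbers censored for each reason by arm.

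The cost is a few lines of text. The times to first dose are already collected; the only extra need is the clock time of discharge or withdrawal. The sample size does not change.
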